The Principal Investigator will obtain informed consent from all subjects up to one week prior to their participation in this study. The consent form describes the study and provides sufficient information for subjects to make an informed decision about their participation in this study. The principal investigator or his designee will discuss the study with the subject. Patients with mild AD (MMSE \geq 20) are able to understand a consent form and over 95% can supply true consent (Buckles et. al, Neurology 2003). Participants will be reminded at the start of each session that they may discontinue at any time and that this will not affect their care in any way. In addition, we will engage a health care proxy, spouse, or close family member, where available. The subject will be given time to read the consent form and to ask questions. Upon entry into the study, the subject or surrogate will receive a copy of the consent form, and a copy will be filed with their study binder.

B7. STUDY LOCATION

Privacy

The subjects' privacy will be protected by ensuring that the conditions under which information will be collected afford protections against interactions with participants being witnessed, overheard or inadvertently intercepted or viewed. Furthermore, the information being collected will be minimized to include only the data necessary to accomplish the research.

A unique identifier code will be assigned to each subject. All information, including EEG data files, will be stripped of personal identifying information. Patient confidentiality will be strictly maintained, and results of all testing will be available only to subjects and/or their health care providers, if requested by the subjects.

Physical Setting

Study sessions will in the Clinical Research Center on the East Campus of BIDMC. MRI scans will be conducted in the Research Radiology department in an adjoining building (Rabb Building). Drug administration will take place at the Clinical Research Center and the Research Pharmacy will be responsible for counterbalancing.

B8. DATA SECURITY

Information about study subjects will be kept confidential and managed according to the requirements of the Health Insurance Portability and Accountability Act of 1996 (HIPAA). Those regulations require a signed subject authorization informing the subject of the following:

- What protected health information (PHI) will be collected from subjects in this study
- Who will have access to that information and why
- Who will use or disclose that information
- The rights of a research subject to revoke their authorization for use of their PHI.

In the event that a subject revokes authorization to collect or use PHI, the investigator, by regulation, retains the ability to use all information collected prior to the revocation of subject authorization.

Subject binders will be kept in a locked cabinet accessible only to the investigators. For data analysis, data will be entered into a password-protected computerized database behind the BIDMC firewall. The investigator will retain study essential documents for at least 2 years after completion of the study.

General Safety

All safety considerations were included as part of the design of this study.

Data Safety Monitoring Plan

Monitoring of Adverse Events: While levetiracetam is not used in treating Alzheimer's disease, it is widely used in the treatment of epilepsy, including epilepsy that develops in patients with Alzheimer's disease. We will be using a single dose, so the risk of side effects is low.

Participants will complete the side effects questionnaire prior to and after every session in order to evaluate side effects.

The occurrence of any unexpected undesirable side effect will result in holding the trial until communication with the IRB, the CRC administrative staff, and the Research Subject Advocate

has taken place, and the risk for participants reassessed. Participation in the study for any given participant will stop in the event of any unexpected side effects or any cognitive deterioration as measured by the serial assessments described above.

Reporting of Adverse Events: All adverse events will be reported and reviewed every week according to laboratory policies. Information about all adverse events relating to this study will be collected and reported on the attached Report of Adverse Event Form. Any adverse event occurring in participants after they sign the consent form and until two weeks after the trial will be reported according to the following guidelines:

- (1) All fatal, life-threatening or serious adverse events will be reported verbally ([name]) and faxed ([name]) to the CRC RSSO Director and the CCI within 24 hours.
- (2) Unexpected serious adverse events will be reported verbally in real time to the CCI and the CRC RSSO Director.
- (3) Unexpected moderate adverse events will be reported in writing to the CCI and the CRC RSSO Director within 10 days of occurrence or recognition.

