In our previous study of 22 AD participants (mean age=75.6, MMSE 22.2) and 16 demographically matched controls (mean age=72.6, MMSE 27.9), we measured hippocampal, amygdala, and parahippocampus CBF as a % of visual cortex. In addition, we corrected for atrophy on a voxel-by-voxel basis by measuring gray matter volume in each voxel using T1 maps that were acquired in the same sequence as the perfusion maps. A region of interest analysis was performed using an *a priori* template, with left and right regions averaged together. The table below shows the results of the atrophy-corrected perfusion measurements as a percentage of visual cortex perfusion.

	Hippocampus	Amygdala	Parahippocampus
Mean AD (SD)	0.96 (0.29)	0.61 (0.19)	0.74 (0.20)

Mean CN (SD)	0.77 (0.17)	0.52 (0.11)	0.62 (0.14)
Prob of difference	0.008	0.043	0.017

Choice of levetiracetam as a pharmacologic probe

In this pilot study, we aim to determine whether the hippocampal hyperperfusion seen on ASL-MRI reflects abnormal epileptiform activity by using levetiracetam as a pharmacological probe. Even intermittent epileptic discharges, in the absence of clinically obvious seizures, may lead to memory impairment. If so, a reduction of hippocampal epileptiform activity could improve declarative memory and potentially alter progression of AD.

Levetiracetam, a newer antiepileptic drug, decreases the frequency and limits propagation of epileptiform activity without affecting normal neuronal excitability^{28, 29}. The mechanism of action of levetiracetam is not fully understood, but it binds specifically to synaptic vesicle protein SV2A and likely modulates its function³⁰. Levetiracetam may also have an indirect effect on GABA-A inhibitory neurotransmission and on high-voltage activated calcium channels. Levetiracetam decreases cortical excitability measured by transcranial magnetic stimulation³¹. In a study of levetiracetam in photosensitive epilepsy, 250mg oral doses decreased epileptiform activity induced by photic stimulation within 1 hour, and 750mg oral doses completely abolished epileptiform activity³². Acute dosing of levetiracetam 500mg caused significant reduction in the frequency of interictal epileptiform activity in 8/10 patients with epilepsy³³. Because of its rapid onset of action and effect on interictal epileptiform activity as well as seizures, levetiracetam is an excellent candidate AED to examine changes in perfusion on ASL-MRI.

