Levetiracetam is FDA-approved for the treatment of partial epilepsy in adults and children > age 4 years. Levetiracetam has a serum half-life of 10-11 hours in healthy elderly subjects³⁴. Excretion is 100% renal; the half-life is prolonged in patients with renal impairment. There is no significant plasma protein binding. Because levetiracetam is not metabolized by hepatic microsomal P450 enzymes, it has no known drug interactions and kinetics are linear³⁵. Levetiracetam intravenous infusion is bioequivalent to oral tablets³⁶.

Cognitive effects of acute administration of levetiracetam have been studied in healthy volunteers, ages 20-50 years³⁷. There was no difference between levetiracetam and placebo in the summary score for the cognitive neurophysiologic test (CNT), which combines electroencephalography (EEG), evoked potential (EP), and cognitive performance measures.

Levetiracetam is a well-tolerated and safe AED in elderly patients. In 166 elderly patients with cognitive disorders (post-stroke or post-traumatic cognitive disorder or memory disorders), asthenia (16.9%), somnolence (7.8%), headache (7.2%), and dizziness (7.2%) were the most common adverse effects³⁵. In an open label phase IV study of patients > 65 years with epilepsy, approximately 40% of patients reported one or more adverse events, usually mild or moderate in severity, with 19.2% discontinuing levetiracetam because of side effects³⁸. Somnolence (16.7%) and dizziness (9%) were the most commonly reported adverse effects. In 24 cognitively impaired elderly patients with epilepsy treated with levetiracetam for 12 weeks, significant overall improvements were observed for the Folstein's Mini-Mental State Examination and the Alzheimer's Disease Assessment Scale-Cognitive³⁹. A study comparing AED retention rates in patients > age 55 found levetiracetam to have the second-highest one-year retention and seizure-free rate (73%), at a median daily dose of 1500mg⁴⁰. In an open label study in

patients with AD and epilepsy, levetiracetam was effective and well tolerated⁴¹. Of 25 patients with severe AD treated with levetiracetam 1000–1500 mg daily, 72% were seizure-free for at least one year, 16% discontinued for adverse effects, 8% were unresponsive, and 4% were lost to follow-up.

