Data on acute use of intravenous levetiracetam in elderly patients is limited. Levetiracetam is well tolerated in healthy young subjects (< 65 years) after 15 minute (2000-4000mg) and 5 minute (1500-2500mg) infusions⁴². One retrospective observational study included 14 older patients (mean age 73.9 years) with a series of complex partial seizures or convulsive or non-convulsive status epilepticus needing emergent intravenous (IV) treatment⁴³. Seizure control was achieved in 11/14 patients (78.6%) at a mean dosage of 1,643 mg/day (range 500-4,000). The only adverse effect was sedation.

Levetiracetam was recently tested in animal models of AD and in adults with mild cognitive impairment. Levetiracetam 5 mg/kg reduced epileptiform discharges and improved memory performance in hAPP mice, while sodium channel blocking AEDs resulted in worsened memory performance. In a recent study in patients with mild cognitive impairment, levetiracetam 250mg twice daily for two weeks normalized hippocampal hyperperfusion, as measured by blood oxygen level dependent (BOLD) MRI. For this study, we chose two doses of levetiracetam (low 2.5 mg/kg and high 7.5 mg/kg) based on the information above.

B3. DESCRIPTION OF RESEARCH PROTOCOL

A. Study Design – Overview, Methods, Procedures

1. Study Overview

This double-blind, within-subject crossover pilot study will test whether increased hippocampal perfusion on ASL-MRI in AD is caused by epileptiform activity. If epileptic activity is occurring and impairing hippocampal function, then levetiracetam should lead to decreased rCBF in the hippocampus and improved declarative memory.

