We will do two analyses, one focused specifically on hippocampal perfusion and a second analyzing regional CBF throughout the whole brain. First, we will use a repeated measures ANOVA with hippocampal perfusion and session (placebo, 2.5mg/kg and 7.5mg/kg) being the factors. Hippocampal perfusion is measured as a percentage of visual cortex perfusion, using a template available within the Statistical Parametric Mapping package. Second, we will measure regional CBF throughout the whole brain using SPM5 and measure changes after drug vs. placebo using a random effects model and accounting for the repeated measures design. In addition to direct analysis of perfusion, we will examine cortical changes in CBF correlated with our seed region in the hippocampus. We predict that decreases in perfusion in the hippocampus after levetiracetam will correlate with increases in perfusion in association cortical regions. Lastly, we will test for correlations between behavioral measures of memory and regional changes in CBF in hippocampus and whole brain. We predict that decreases in hippocampal perfusion will paradoxically correlate with improved declarative memory performance.

EEG Data

EEG will be visually analyzed for presence of epileptiform activity. Peak alpha power, beta band power, delta/theta power, and coherence will be calculated using BESA (Brain Electrical Source Imaging) software and Persyst MagicMarker software. Measures will be analyzed using repeated measures ANOVA. We hypothesize that levetiracetam will decrease source coherence in temporal regions.

Analyses will be performed in the Cognitive Neurology Unit, Magnetic Resonance Imaging Center of the Department of Radiology, and EEG Laboratory at Beth Israel Deaconess Medical Center.

C. Subject Selection

Subjects will be recruited from the Cognitive Neurology Unit at BIDMC. The P.I., who specializes in neurodegenerative disorders, maintains an active clinic and treats over 100 patients with AD. In addition, the Cognitive Neurology Unit has over 13,000 patient visits per year.

Inclusion Criteria:

- Meets the NINCDS-ADRDA criteria for probable Alzheimer's disease
- Mild AD (MMSE \geq 20)
- Age \geq 50 years
- English as first language

Exclusion Criteria:

- A history of seizures prior to the onset of AD
- Familial Alzheimer's Disease due to known genetic mutations
- Current use of an anti-epileptic medication

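### Hypothesis 1 predicts a fall in perfusion after levetiracetam, but the plan names no dose-versus-placebo contrast for perfusion, whole-brain flow or memory

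*Combined protocol and SAP*

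**What the plan says.** B1 (Aim 1, Hypothesis 1) predicts that hippocampal perfusion will fall after levetiracetam and not after placebo. No dose is named. Two doses are studied, and B2 (Choice of levetiracetam as a pharmacologic probe) gives their basis: "For this study, we chose two doses of levetiracetam (low 2.5 mg/kg and high 7.5 mg/kg) based on the information above".

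B3.B, Data Analysis, then sets out three relevant tests:

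- **Hippocampal perfusion (primary).** A repeated measures ANOVA with placebo, 2.5 mg/kg and 7.5 mg/kg as the levels of session. No contrast, order of testing or follow-up test is given.
- **Whole-brain regional flow (secondary).** The plan will "measure changes after drug vs. placebo using a random effects model and accounting for the repeated measures design". It does not say whether this is one dose, each dose in turn, or both averaged.
- **Memory (primary).** The main hypothesis is better memory performance following drug, again with no dose. The primary memory score, named in B3.A under Behavioral testing, is free recall on the Free and Cued Selective Reminding Test (FCSRT).

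The Sample Size Justification claims a 72% chance of detecting a decrease after levetiracetam with 20 participants, also without naming a dose.

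**The concern.** With three conditions, the comparison of drug with placebo is not one comparison. It could be high dose, low dose, either, or the average of the two. The plan leaves this open for both primary outcomes and for the whole-brain analysis, so the choice could be made after the data are seen.

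The three-level F does not settle it. It is undirected and is significant for any pattern of differences among the three means, including a rise in perfusion or a difference between the two doses only. A significant result would therefore not establish Hypothesis 1, and would not say which dose was responsible.

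There is also a cost in power when the effect is graded by dose. B2 itself cites such a pattern in photosensitive epilepsy: "250mg oral doses decreased epileptiform activity induced by photic stimulation within 1 hour", while "750mg oral doses completely abolished epileptiform activity". If the low dose acts partially, the F is weaker than the direct comparison of high dose with placebo.

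**Working it through.** **Inputs from the documents.** N = 20 and 72% power (Sample Size Justification). Hippocampal ratio 0.96 (SD 0.29) in AD and 0.77 (SD 0.17) in controls (B2 table). Effect 0.96 − 0.77 = 0.19, since the drug is assumed to lower perfusion only to normal.

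**Assumptions.** Two-sided alpha 0.05 (not stated in the plan); equal variances and equal correlations across the three conditions; low-dose effect equal to a fraction f of the high-dose effect.

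**Step 1: reproduce the plan's figure.** Average SD = √((0.29² + 0.17²)/2) = 0.2377. For two independent groups of 20, 0.19 / (0.2377 × √(2/20)) = 2.528. Normal-approximation power = Φ(2.528 − 1.96) = 71.5%, which matches 72%. So the plan's figure is a single comparison of drug with no drug, with no credit for within-subject correlation.

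**Step 2: set the direct contrast at 72%.** In the repeated measures model the error df are (20 − 1) × (3 − 1) = 38. Power of 72% for F(1, 38) needs noncentrality λ = 6.81 for high dose against placebo.

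**Step 3: noncentrality of the other two tests.** With mean changes 0, fδ and δ:

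- Three-level F(2, 38): λ = (4/3) × 6.81 × (1 − f + f²)
- Average of both doses against placebo, F(1, 38): λ = 6.81 × (1 + f)² / 3

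| Low-dose effect f | λ, three-level F | Power | λ, doses averaged | Power | High vs placebo |
|---|---|---|---|---|---|
| 0 (inert) | 9.08 | 74% | 2.27 | 31% | 72% |
| 1/3 | 7.06 | 62% | 4.03 | 50% | 72% |
| 1/2 | 6.81 | 61% | 5.11 | 60% | 72% |
| 1 (fully active) | 9.08 | 74% | 9.08 | 84% | 72% |

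**Step 4: vary the variance.** The SD of a within-subject difference is not in the documents. With zero correlation it is √(0.29² + 0.17²) = 0.336. The values 0.29 and 0.20 are assumptions. For each, λ for high against placebo = 20 × 0.19² / SD².

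| SD of difference | High vs placebo | Three-level F, f = 0, 1/3, 1/2, 1 | Doses averaged, f = 0, 1/3, 1/2, 1 |
|---|---|---|---|
| 0.336 | 69% | 71, 59, 58, 71% | 30, 47, 57, 81% |
| 0.29 | 82% | 84, 73, 71, 84% | 38, 59, 70, 91% |
| 0.20 | 99% | 99, 97, 96, 99% | 67, 89, 95, more than 99% |

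The first row gives 69% where Step 1 gave 71.5%, because it uses 38 error df in place of the normal approximation. The pattern is the same in every row, and the gaps narrow as the SD falls.

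**The case against.** The strongest reply is that the primary perfusion analysis already keeps the doses apart. A reader might infer that a weak low dose could hide a high-dose effect there. It would not: with an inert low dose the three-level F has 74% against 72% for the direct contrast. The loss is confined to partial low-dose effects and is about 10 to 11 points. That part of the reply stands in full.

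Second, the low figures of 31% and 50% need the two doses to be averaged, which the plan nowhere states. The whole-brain analysis is also secondary and voxel-wise, so a single-region calculation is not its power. This stands too: those figures show what the ambiguity could cost, not what the plan does.

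Third, the plan itself calls its 72% conservative because a within-subject design should reduce variance. If the SD of the difference were 0.20, the three-level F would have 96-99% throughout and the gain from a direct contrast would be at most about 2 points. What would remain is the question of interpretation: which dose differs, and in which direction.

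A reader might also infer that the stated basis for the low dose fails. The arithmetic behind this is right: 250 mg / 2.5 mg/kg = 100 kg, so anyone lighter receives less than the lowest human dose cited. But B2 cites no result below 250 mg and no dose without effect. The two doses lie either side of the 5 mg/kg mouse dose and keep the 1:3 ratio of 250 to 750 mg. The rationale is brief, but it is not contradicted. Nor does the plan say that a null low-dose result would count against Aim 1.

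**Conclusion.** The point holds as a gap in specification. The plan does not say which dose comparison tests its directional hypothesis, in what order, or whether doses are pooled. This affects both primary outcomes and the whole-brain analysis. The three-level F alone cannot show a decrease from placebo or identify the dose.

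At the plan's own 72%, naming high dose against placebo gains about 10 to 11 points over the F if the low dose has one third to one half of the high-dose effect. It loses about 2 points if the low dose is inert or fully active. These sizes rest on two-sided alpha 0.05, zero within-subject correlation, equal variances across conditions and assumed values of f. They shrink with smaller variance.

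The documents do not show that the low dose is inactive, that it masks a high-dose effect in the primary analysis, or that either dose is wrong. This is an inexpensive improvement, not a flaw that invalidates the design.

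**What to change.** In B3.B, Data Analysis:

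1. **Hippocampal perfusion.** From the same repeated measures model, pre-specify high dose against placebo as the test of Hypothesis 1. If it is significant, test low dose against placebo at the same alpha. A fixed sequence needs no split of alpha. State the alpha and whether tests are one- or two-sided.
2. **Whole-brain flow and FCSRT free recall.** Use the same two contrasts, in the same order, in place of the undefined comparison with drug.
3. **Pooling.** State that doses are not pooled in the main test.

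In B2, reconcile the mg/kg doses with the fixed-mg figures cited there, for example by giving the mg delivered over the expected weight range. No view on dose is offered.

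**Cost.** A few lines of text and no new data. Against the three-level F, about 2 points of power are lost if the low dose is inert or fully active (72% against 74%). Against averaging the doses, about 12 points are lost if the low dose is fully active (72% against 84%). The low dose is not formally tested if the high-dose comparison fails; its estimate and confidence interval can still be reported.
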